Component A. Nurse-led shared decision-making (1 session, <60 min.). AABL persons want and benefit from the opportunity to discuss COVID-19/influenza vaccination with and ask questions of trusted health professionals from AABL backgrounds, such as nurses^{24,31,32,131}. We selected a shared decision making (SDM) approach for this component. SDM is a well-established and acceptable model with a promising empirical evidence base, particularly for affective, cognitive, and longer-term outcomes^{132,133}. SDM is an approach to assist patient decision-making, where clinicians and patients share the best available evidence and where patients are supported to consider options and achieve informed preferences. Instead of assuming that health-related decisions should be guided by scientific consensus about effectiveness, SDM proposes that informed preferences, that is, what matters to patients, should play a major role in decision-making processes^{134,135}. The principles of SDM are well documented and the common elements have been summarized in the literature¹³⁶. In brief, SDM draws on and deepens the principles of patient-centered care^{134,135}. SDM represents an important shift in the roles of both patients and clinicians. SDM recognizes the need to support autonomy by respecting both individual competence and interdependence on others. At its core, SDM is a process where decisions are made in a collaborative way, where trustworthy information is provided in accessible formats about a set of options, typically in situations where the concerns, personal circumstances, and contexts of patients play a major role in decisions^{134,135}. Experts have called for SDM for COVID-19 vaccination decisions¹³⁷⁻¹³⁹. This component uses a practical and empirically-tested SDM model developed by Elwyn and colleagues called the three-step model comprised of team talk, option talk, and decision talk to guide a process of collaboration and deliberation^{134,135}. Theoretical targets: perceived risk and necessity, behavioral intentions.

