We will use a hybrid recruitment plan with active outreach and passive strategies to efficiently the study population. The recruitment approach includes: 1) flyers describing the study in English and Spanish that can be used to directly recruit potential participants using ethnographic street recruitment methods (e.g., recruitment in parks and on the street)¹⁶²; 2) ads placed in the medical research section of free newspapers (e.g., *amMetro, Latino Impact*), 3) ads disseminated on social media and Craig's List, and

4) peer-to-peer recruitment (recruiters will be compensated \$15 for each peer referral, maximum 10 referrals/participant). In past studies, peer-to-peer recruitment was the most efficient and productive recruitment method^{38,83,163}.

Contact form. Potential participants will complete an online contact form linked to a QR code in recruitment materials or they can call the study directly.

Screening for eligibility in two stages. First, verbal informed consent for screening is obtained following an IRBapproved script followed by a brief (< 15 minute) structured screening interview using the **Computer-Assisted Personal** Interview (CAPI) format in REDCap to determine eligibility. Those found eligible will provide locator information. In a second step, documentary evidence of vaccination will be checked and logged. Screening can take place in recruitment venues, the study field site, or virtually (Fig. 3). Those found eligible can enroll.

Enrollment and study activities. Enrollment will take place at a study field site or virtually. Participants will provide electronic signed informed Table 3. Description of the measures in the assessment battery (Phenix toolkit and DR2 will be used where available)

•	
	Moderating influences
Socio-demographics, background factors	Age, race/ethnicity, sex assigned at birth, occupation, sexual/gender minority status, immigration status, preferred language, ZIP code of residence, health status, co- morbidities, racism and discrimination experiences, past COVID-19 diagnosis, vaccination, past influenza vaccination, children in the home
Distrust of vaccination	6-items assessed on a 5-point Likert-type scale 100,166
Counter-narratives (conspiracy theories)	6-items assessed on a 5-point Likert-type scale drawn from existing reliable scales 168,169
	Individual/attitudinal influences
Vaccine and COVID Knowledge	10-item true-false questionnaire on aspects of vaccination, influenza, and COVID-19 ¹⁷⁰

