Perceived risk	Risk of COVID-19 and influenza, 2 items
Necessity of vaccination	Perceived necessity of vaccination for COVID-19 and influenza, 2 items
Behavioral Intentions	Vaccination scenarios assessed with 4 items
Cognitive biases	Measurement of perceived cognitive biases ¹⁰⁵ , engagement in Component B
Motivation/readiness	Importance of COVID/influenza vaccination and confidence in ability to get vaccinated on a 1-100 scale. ¹⁷¹
	Social influences
Peer norms	Assess peer norms re: COVID/influenza vaccination using 6 items ¹⁷²
Altruism & collective responsibility	6 items on COVID/influenza vaccination as an altruistic act/a collective responsibility ¹⁰⁰
	Structural influences
Structural barriers	Perceived structural barriers: insufficient local sites, cost, perceived access
	PRIMARY OUTCOME
COVID-19 vaccination	Documentary evidence, date, name of vaccine(s), place of vaccination(s)
	SECONDARY OUTCOME
Influenza vaccination	Documentary evidence, date, name of vaccine, place of vaccination
	Intervention process domains
Acceptability	Client Satisfaction Questionnaire (YCSQ) –17 items ¹⁷³
Social harms	Assessment of possible harms experienced in social, occupational domains.
	Feasibility/Intervention dose
Intervention dose	Attended core, Component A: Component B: number of TM responses; Component C: size of prize; Component D: number of navigation contacts completed and their characteristics/content

consent in REDCap (using the "eConsent" feature) for enrollment (or verbal consent if virtual), complete a more detailed locator form to facilitate longitudinal FU, and participate in a structured BL interview in REDCap. They will be randomly assigned to an experimental condition using REDCap. Participants have the opportunity to engage in the core session on the same day, or as soon as possible (ideally within 1-2 weeks). Then, other assigned components will be administered.

Assessment battery in REDCap (Table 3). The BL will last ~30-45 minutes. Follow-up (FU) assessments will be carried out 3- and 6-months post-BL. FU interviews last ~25-35 minutes. BL interviews will assess the lifetime and past 3-month period, and the FUs will assess the period since the last interview^{118,119}.

At 12-months post-baseline we will check COVID-19 and influenza vaccination status by self-report and with documentary evidence for COVID-19.

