Aim 1: Identify which of four candidate intervention components contribute meaningfully to improvement in the primary outcome, receipt of the available COVID vaccine, with documentary evidence at the 6-month FU. The primary outcome for Aim 1 is receipt of the available COVID vaccine (documented) by the final follow-up. Logistic regression will estimate effects of components on the odds of receiving the available COVID vaccine. Intervention components will be effect-coded to estimate main effects and interactions of all four components (see **Equation 1**). The coefficient for an effect-coded main effect term (e.g., *b₁*), multiplied by two and exponentiated, will estimate the effect of the component (e.g., Component A) on the odds of vaccination. Similarly, the coefficient for an effect-coded interaction term, multiplied by two and exponentiated, will estimate interaction effects on the odds of vaccination. Similar logistic regression analyses will estimate effects on the secondary outcome.

Equation 1

$$\log\left(\frac{\pi_i}{1-\pi_i}\right) = b_0 + b_1 X_A + b_2 X_B + b_3 X_C + b_4 X_D + b_5 X_{A*B} + b_6 X_{A*C} + b_7 X_{A*D} + b_8 X_{B*C} + b_9 X_{B*D} + b_{10} X_{C*D} + b_{11} X_{A*B*C} + b_{12} X_{A*B*D} + b_{13} X_{A*C*D} + b_{14} X_{B*C*D} + b_{15} X_{A*B*C*D}$$

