Aim 2: Identify mediators and moderators of the efficacy of each intervention component. To examine potential mediators, analysis for Aim 2 will use the potential outcomes framework¹⁸⁹⁻¹⁹¹. This framework highlights assumptions needed to identify direct and indirect effects of interest: no unmeasured cofounders of the exposure (an intervention component) and outcome (vaccination) relation; no unmeasured confounders of the mediator and outcome relation; no unmeasured confounders of the exposure and mediator relation; and no measured or unmeasured confounders of the mediator and outcome relation affected by exposure. Since intervention components are randomly assigned, the key issue for the proposed study is addressing confounding of the relation between mediators and outcomes. Mediators measured at baseline will be included as confounders of the relation between follow-up mediators and vaccination. Sensitivity analysis will determine how the size of the correlation between error for the mediator model and error for the outcome model impacts inferences for direct and indirect effects. The total natural indirect effect (TNIE) and pure natural direct effect (PNDE) of each component will be estimated using the mediation R package¹⁹². The TNIE compares the outcome when subjects are exposed (e.g., receive a component), and the mediator varies as it would naturally under exposure, versus the outcome when subjects are exposed but the mediator varies as it would naturally in the absence of exposure (i.e., component not received). The PDNE compares participants at different levels of a component (e.g., On vs. Off) when a mediator is

blocked. Potential moderator effects will be examined by adding interaction terms to the model described for **Aim 1**. We will include sociodemographics and other covariates (e.g., medical distrust) and explore the interactions of these variables with intervention components. When interaction effects are detected, we will estimate the simple main effects of the intervention component. Identified moderators will inform dissemination and future adaptive interventions¹⁹³.

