Aim 3: Build the most cost-effective intervention package(s) from the components found to be efficacious in Aim 1. We will estimate the total cost of each experimental condition, rank them low to high, and remove any due to dominance (higher cost with lower effectiveness). Then, we will calculate the incremental cost-effectiveness ratio comparing each condition with the next lower cost condition, $[(cost_1 - cost_2)/(outcome_1 - outcome_2)]$, to yield for each component the *incremental cost per participant receiving vaccination* and *incremental cost per percentage point change in vaccination rate* (from Aim 1); we also will explore the *incremental cost per participant*.

The decision-making process will be led by [name] and include the study Co-Investigators ([name], [name], [name], [name], [name]) and consultants³⁵. The decisions will be reviewed with the CAB before being finalized. STEP 1: Carry out Aim 1 analyses, which detail the effectiveness of each component (% vaccinated) as well as interaction effects. This allows us to predict % vaccinated for each experimental condition, adjusting for any covariates. STEP 2: Carry out Aim 2 analyses, gualitative analyses, and the joint display to determine how components work and under what conditions, along with acceptability and feasibility. These data will be integrated into the implementation manual. STEP 3: Use cost estimates and incremental cost-effectiveness ratios from Aim 3 and rank-order experimental conditions by incremental cost-effectiveness ratio. STEP 4: Carry out same steps for influenza and consider that in decision-making. FINAL STEP: There may be several good options for improving outcomes at different levels of cost. We will create an efficient frontier for these experimental conditions using methods developed by our colleagues at NYU called decision analysis for intervention value efficiency (DAIVE), a decision-making framework for use in MOST²⁰¹. DAIVE is a user-friendly method for evaluating interventions based on a wide variety of decision-maker preferences, including those that involve multiple outcome variables. We have used DAIVE in a past study²⁰¹. Using data from the previous steps as inputs, DAIVE will be used to create an efficient frontier of interventions for COVID alone, influenza alone, and COVID and influenza together (where we can

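### Equation 1 tests the components without any baseline covariate; a short fixed list would change power by about 0 to +4 points at almost no cost

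*Combined protocol and SAP*

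**What the plan says.** The Aim 1 paragraph of the quantitative data analysis section gives the primary model: "Logistic regression will estimate effects of components on the odds of receiving the available COVID vaccine". Equation 1 writes it out in full, with an intercept and all 15 effect-coded main effects and interactions of the four components. It has no covariate, and the Power Analysis paragraph names none.

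The paragraph on enrollment and study activities describes the baseline interview before assignment: participants "participate in a structured BL interview in REDCap. They will be randomly assigned to an experimental condition using REDCap". Table 3 lists the battery, which includes:
- behavioral intentions: "Vaccination scenarios assessed with 4 items";
- motivation/readiness, which includes "confidence in ability to get vaccinated on a 1-100 scale";
- background factors, among them "past COVID-19 diagnosis, vaccination, past influenza vaccination".

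Covariates appear elsewhere in the plan. Aim 2 says: "Mediators measured at baseline will be included as confounders of the relation between follow-up mediators and vaccination". Intentions are one of these mediators; for Component A the plan gives "Theoretical targets: perceived risk and necessity, behavioral intentions". Aim 2 also adds sociodemographic and other covariates, but in its moderator models. Step 1 of the Aim 3 decision process says of the Aim 1 results: "This allows us to predict % vaccinated for each experimental condition, adjusting for any covariates". No list is given there or anywhere else for the primary test.

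**The concern.** Adjusting a randomised comparison for strong baseline predictors of the outcome usually sharpens the test of treatment without adding participants. Here the predictors are collected anyway. By using baseline mediators as confounders of the mediator-vaccination relation, the plan itself presumes in Aim 2 that they are related to vaccination. The Aim 1 test does not use that information.

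Two things are at stake. The first is a somewhat higher chance than necessary of missing a useful component. The second is that the percentages feeding the Aim 3 cost-effectiveness ratios refer to covariates that nobody has named.

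**Working it through.** **1. The plan's own power figure.** Inputs from the Power Analysis paragraph are 448 analysed, overall uptake 40%, odds ratio 1.9 and α = .05 (taken as two-sided). The study design section compares 8 conditions with 8 for each main effect, so 224 with 224. Rates that average 40% with odds ratio 1.9 are 32.4% (off) and 47.6% (on).

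SE of the log odds ratio = √[1/(224 × 0.3237 × 0.6763) + 1/(224 × 0.4763 × 0.5237)] = √(0.0204 + 0.0179) = 0.196.

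Power = Φ(ln 1.9/0.196 − 1.96) = Φ(3.28 − 1.96) = 90.7%; a pooled two-proportion test gives 91.2%. The plan states 87%. An unstated assumption can bring the figure close: with all four components at odds ratio 1.9 in Equation 1, power is 88.0%.

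**2. One baseline score added to Equation 1, marginal odds ratio held at 1.9.** The strength of the score is assumed.

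| Odds ratio per SD of score | AUC | R² | Power without → with | Gain (points) |
|---|---|---|---|---|
| 1.2 | 0.56 | 0.01 | 90.7 → 90.9% | 0.2 |
| 1.5 | 0.61 | 0.03 | 90.7 → 91.5% | 0.9 |
| 1.8 | 0.66 | 0.07 | 90.7 → 92.5% | 1.8 |
| 2.2 | 0.70 | 0.11 | 90.7 → 93.5% | 2.9 |
| 2.7 | 0.74 | 0.15 | 90.7 → 94.6% | 4.0 |

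Gains are computed before rounding. Simulation of the full Equation 1 with one score and three useless covariates agrees. Power went from 91.4 to 91.5% (useless score), 91.4 to 93.0% (log-odds SD 0.6) and 91.7 to 95.7% (SD 1.0).

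**3. Starting from the stated 87%.** Power = Φ[(1.96 + 1.126)/√(1 − R²) − 1.96]. For R² = 0.03 this is 88.0%; for 0.10 it is 90.2%; for 0.125 it is 91.0%. The gain is again 1 to 4 points.

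**4. A whole covariate list.** In 40,000 simulated trials per scenario, five terms were added: an intentions score with reliability 0.7, two terms for three enrolment periods, past influenza vaccination (9%, the past-year figure from the team's COVID testing study), and more than one prior COVID-19 dose (60%, assumed).

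| Assumed strength | Power | Variance ratio of the risk difference | Equivalent n = 448/ratio |
|---|---|---|---|
| Useless | 91.5 → 91.3% | 1.013 | 442 |
| Moderate | 91.5 → 92.9% | 0.951 | 471 |
| Strong | 91.7 → 95.4% | 0.849 | 528 |

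With the intentions effect mis-specified and 10% of scores missing, the gains fall to 0.8 points (moderate) and 2.4 points (strong). Type I error was 5.4% with and without adjustment.

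**5. Without the prior-dose item.** The list recommended below drops it unless the vaccination record supports it. Its share of the assumed log-odds variance is small. In the moderate case it is 0.6 × 0.4 × (ln 1.5)² = 0.039 of 0.61² = 0.37. In the strong case it is 0.24 × (ln 2)² = 0.115 of 1.18² = 1.39. That is about a tenth, so the gains of 1.4 and 3.7 points shrink only slightly.

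**6. Change of target.** A marginal odds ratio of 1.9 corresponds to a covariate-conditional one of about 1.95 to 2.26 over the moderate to strong settings.

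**The case against.** Several objections have force.

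- **The gain rests on assumed strength.** The documents give none. In the related COVID testing study 13% intended to get boosters and about 2% were vaccinated during follow-up, so at most about 2/13 = 15% of intenders were. That study did not intervene on vaccination, so it does not show that intentions predict poorly, but it lends no support to the strong scenario either. The range must include zero.
- **Past COVID-19 vaccination is constant.** Eligibility criterion 5 requires at least one dose, so a yes/no term would be collinear with the intercept. This stands, and the fix avoids it.
- **Power is only part of the decision.** The plan states no significance rule for Aim 1, and Aim 3 also weighs predicted percentages, costs and decision-maker preferences. This stands.
- **Low uptake is the larger threat to a 16-cell model.** At 20% uptake (the lowest bivalent-booster figure in the Significance section) about 8% of simulated datasets had an empty cell; at 10% the figure is about 71%. Adjustment does not cure this. At 20% it still moved power from 68.9 to 68.8% (useless), 69.0 to 70.6% (moderate) and 68.7 to 74.0% (strong).

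A reader might infer more than the documents support. The unadjusted test is not biased or invalid, because assignment is random. Nor is the trial shown to be underpowered for want of covariates: the literal inputs give about 91%, and the stated 87% is the more cautious figure. The reference to covariates in Aim 3 may mean only adjustment if there are any; it does not show that they will be chosen after the outcomes are seen.

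**Conclusion.** The point holds as a modest, nearly free gain in precision. Under the plan's assumptions, adjustment changes power for one component by about -0.2 points (useless covariates), +1 to +2 (moderate) or +4 (strong). The result rests on assumed predictor strength (R² of about 0.03 to 0.15 for a gain of 1 to 4 points), a marginal odds ratio of 1.9, and baseline measures taken before assignment, as the text's order indicates. Naming the covariates has a value that does not depend on their strength: it settles which model produces the Aim 3 percentages.

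**What to change.** Add to Equation 1 a fixed list:
1. the baseline behavioral intentions score, named as one score with its scoring rule;
2. past influenza vaccination, with its reference period stated;
3. enrolment period, grouped by which COVID-19 vaccine was the available one at enrolment. The plan expects that vaccine to change, and implementation and evaluation last 34 months.

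Include COVID-19 vaccination history only as a defined prior-dose count or time since last dose, and only if the vaccination record gives it. Handle missing covariates with the multiple imputation already planned.

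Test each component on its adjusted coefficient and report the covariate-standardised risk difference beside the conditional odds ratio. Use the same model and standardisation for the Step 1 predictions in Aim 3, replacing the open reference to covariates. Keep unadjusted Equation 1 as a supporting analysis.

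The cost is analysis-plan wording. The first two measures are in the baseline battery, and the enrolment date should be on record. The downsides are that the odds ratio becomes conditional, so the target must be named in advance, and that a fraction of a point of power is lost if the covariates prove useless.

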Power Analysis. For the primary outcome, vaccination with the available COVID vaccine, we used PASS 2023¹⁹⁴ to estimate the sample size needed for main effects of intervention components corresponding to odds ratios of 1.9 in logistic regression, given α =.05. Assuming a 40% chance of vaccination by the final follow-up overall, a sample size of n=448 (n=28 in each of 16 conditions) provides 87% power to detect an odds ratio of 1.9. To account for attrition of up to 20%, we propose a total sample size of 560 participants (n=35 in each of 16 conditions), ensuring complete data for at least n=28 per condition. When the main effect of an intervention component on a continuous mediator is estimated in a linear model, the sample size provides 80% power to detect a small standardized mean difference (d = .27). Moderator effects corresponding to an odds ratio of OR=1 in one subgroup and OR=4 in another can be detected with 83% power if subgroups sizes are roughly equal. To estimate the size of a mediated effect that can be detected given the proposed sample size, we use the approach described by Vittinghoff and colleagues¹⁹⁵ as implemented in PASS 2023. Given a substantial correlation between an intervention component and a hypothesized mediator (*r*=.50), an odds ratio of 1.40 can be detected with >80% power for the effect of a mediator on the vaccination outcome.

Qualitative data analysis and integration. Qualitive analyses will focus on experiences with the candidate intervention components, to inform intervention implementation and future research. Coding and analytic methods of qualitative data will employ a directed content analysis approach¹⁹⁶. Analyses will begin with pre-determined codes based on the conceptual model (i.e., a "start list"), which will be expanded based on emergent findings. We will attend to trustworthiness and rigor. Integration of qualitative/quantitative results will use the joint display method¹⁹⁷. A joint display is a state-of-the-art visual tool to integrate data sources¹⁹⁸⁻²⁰⁰.

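### The stated >80% power for a mediator odds ratio of 1.40 omits the baseline mediator in the Aim 2 model; at r=.50 it drops below 80% once the baseline-to-follow-up correlation exceeds about .32 to .37

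*Combined protocol and SAP*

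**What the plan says.** The Power Analysis section gives one power figure for mediation: "an odds ratio of 1.40 can be detected with >80% power for the effect of a mediator on the vaccination outcome". The condition attached to it is "Given a substantial correlation between an intervention component and a hypothesized mediator (*r*=.50"). No other correlation is named. The method is a published sample-size approach for mediation, run in PASS 2023.

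The other inputs come from the same section: "Assuming a 40% chance of vaccination by the final follow-up overall"; "a sample size of n=448 (n=28 in each of 16 conditions"); and, for enrolment, "To account for attrition of up to 20%, we propose a total sample size of 560 participants". The significance level appears with the main-effects calculation, "corresponding to odds ratios of 1.9 in logistic regression, given α =.05".

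The Aim 2 analysis text specifies the model: "Mediators measured at baseline will be included as confounders of the relation between follow-up mediators and vaccination". The outcome model for a mediator therefore holds the component, the follow-up mediator and the baseline value of that mediator.

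**The concern.** Power for the mediator coefficient in a logistic model depends on how much mediator variance is left after every other term in the model has been accounted for. The Power Analysis removes only the share explained by the component. The Aim 2 model also removes the share explained by the baseline value of the same construct. These are self-report measures (intentions, norms, altruism and similar) repeated at 3 and 6 months, so that share need not be small.

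Mediation is one of the two parts of Aim 2. STEP 2 of the Aim 3 decision process uses the Aim 2 results to describe how components work and carries them into the implementation manual. A null mediator result would be judged beside a power figure that may not belong to the model fitted.

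**Working it through.** **Inputs from the documents.** Completers N = 448; uptake p = .40; odds ratio 1.40; component-mediator r = .50, so R² = .25; α = .05.

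**Assumptions.** The odds ratio is per 1 SD of the mediator, and the test is two-sided; the plan states neither. N = 448 is used because the same section's 80% power for d = .27 fits 448 (computed 81.5%) better than 560 (89.2%).

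**Formula.** Power = Φ( ln(OR) × √[N p (1−p)(1−R²)] − 1.96 ). Here N p (1−p) = 448 × .4 × .6 = 107.52 and ln(1.40) = .3365.

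**Step 1: reproduce the plan's figure (no baseline mediator).** √(107.52 × .75) = 8.980; .3365 × 8.980 = 3.02; 3.02 − 1.96 = 1.06; Φ = 85.6%. This agrees with >80%.

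**Step 2: largest R² that keeps 80%.** The requirement is .3365 × √[107.52(1−R²)] = 1.96 + .8416 = 2.8016. Hence 1−R² = .645 and R² = .355.

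**Step 3: add the baseline mediator.** The component is randomised and so independent of the baseline value. Let rb be the correlation of the baseline with the follow-up mediator.

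- Marginal rb (pooled over component on and off): R² = .25 + rb². Break-even rb = √(.355 − .25) = .32.
- Within-arm rb: 1−R² = .75(1−rb²). Break-even rb = √(1 − .645/.75) = .37.

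The rb values below are assumptions, because the documents give none.

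| rb | Power, marginal | Power, within-arm |
|---|---|---|
| .2 | 83.6% | 84.1% |
| .3 | 80.9% | 82.2% |
| .4 | 76.4% | 79.1% |
| .5 | 69.4% | 74.4% |
| .6 | 58.7% | 67.6% |

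**Step 4: simulation check.** Logistic models were simulated with 2,000 runs per setting, N = 448 and marginal rb of .4/.5/.6. With the baseline mediator in the model, power was 75.8/67.2/58.3%. Without it, power was 84.9/85.5/82.3%. The formula is close enough for this purpose.

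**Step 5: a smaller component effect.** The section's own d = .27 corresponds to r = .134 and r² = .018. With the baseline mediator included, marginal rb of .4/.5/.6 gives 88.6/84.7/78.6%. Break-even rb = √(.355 − .018) = .58.

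**Step 6: odds ratio detectable with 80% power at r = .50, N = 448.** OR = exp( 2.8016 / √[107.52(1−R²)] ).

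| rb | 1−R² marginal | OR | 1−R² within-arm | OR |
|---|---|---|---|---|
| .4 | .59 | 1.42 | .63 | 1.41 |
| .5 | .50 | 1.47 | .5625 | 1.43 |
| .6 | .39 | 1.54 | .48 | 1.48 |

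**The case against.** The strongest reply is that the stated figure is right on its own inputs, and that any shortfall comes from a correlation the documents never give. Both parts are true. A reader might infer that the plan contains an arithmetic error, or that the planned model has 59 to 76% power. The documents support neither. The first fails because 85.6% satisfies >80%. The second takes only marginal correlations of .4 to .6: at .3 power is still 81%, and the same .4 to .6 read as within-arm values gives 79 to 68%. The choice of reading matters, since at r = .50 a marginal .6 is a within-arm .6/√.75 = .69.

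It can also be said that r = .50 is a demanding condition. It corresponds to d of about 1.15, and in this formula a larger r lowers power. At d = .27 the planned model keeps about 79 to 89%. This stands as a limit on scope. It does not rescue the published statement, which is made at r = .50 and does not say that this value was chosen to leave room for other covariates.

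The section also refers to the proposed sample size, which could mean 560. At 560 completers the marginal break-even rises to about .48 and power is 85/79/68% at .4/.5/.6. The d = .27 figure points to 448, and 560 would require no attrition.

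Finally, nothing in the documents says that a null mediator will be taken as proof of no mechanism. STEP 2 sets mediation beside qualitative work and a joint display. The consequence is therefore a risk of misreading and does not touch component selection, which rests on Aims 1 and 3.

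**Conclusion.** The concern holds in a limited form. The power statement and the Aim 2 model do not match: one allows for the component alone, while the other adds the baseline mediator. The >80% is correct for the model without the baseline value. For the planned model at r = .50 it holds only while the baseline-to-follow-up correlation stays at or below about .32 (marginal) or .37 (within-arm). Whether it is exceeded cannot be settled from the documents.

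The shortfall is specific to the r = .50 condition and should not be generalised to smaller component effects. The result rests on 448 completers, 40% uptake, an odds ratio per SD and a two-sided .05 test. The primary sample size and the Aim 1 analysis are unaffected.

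**What to change.** Keep the baseline adjustment; it addresses the mediator-outcome confounding that Aim 2 itself identifies as the key issue. Change the Power Analysis instead:

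- Compute mediation power from the multiple R² of the follow-up mediator on the component plus its baseline value.
- State the assumed baseline-to-follow-up correlation and whether it is marginal or within-arm. Also state the unit of the odds ratio, the sidedness of the test and the N used.
- Restate the result, for example: at r = .50 and N = 448, power is 80% for an odds ratio of about 1.42, 1.47 or 1.54 per SD when the marginal correlation is .4, .5 or .6 (1.41, 1.43 or 1.48 if these are within-arm).

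The cost is a sentence or two and a less favourable published figure. No participants, data collection or analyses are added.
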